**13. Investigator**

Print

Name:

Contact information (address, phone, fax and e-mail): \_\_\_\_\_

Authorized

signature:

Date: |\_\_|\_\_| |\_\_|\_\_| |\_\_|\_\_|\_\_|

## **NARRATIVE SUPPLEMENTAL PAGE**

## 1. Narrative

Provide a clear narrative description of the sequence of events, diagnosis and any other relevant details.

**CONCOMITANT TREATMENT SUPPLEMENTAL PAGE**

2. Concomitant drugs				
Drug name (trade or generic) <small>Include all drugs taken within 2 weeks before onset of the event. Exclude drug used to treat the event.</small>	Therapy continuing	Date (or duration if dates unknown)		Route (e.g. oral, etc.)
		Start (dd/mmm/yyyy)	End (dd/mmm/yyyy)	
	 Yes  No  Unknown			
	 Yes  No  Unknown			
	 Yes  No  Unknown			
	 Yes  No  Unknown			
	 Yes  No  Unknown			
	 Yes  No  Unknown			
	 Yes  No  Unknown			
	 Yes  No  Unknown			
	 Yes  No  Unknown			
	 Yes  No  Unknown			

**PATIENT HISTORY SUPPLEMENTAL PAGE**

**3. Patient history**

Include any other illness present at the time of onset of the event, relevant medical history and pre-existing medical conditions (e.g. allergies, previous drug reaction, alcohol/drug abuse, etc.). Specify disease entity for each drug listed in the concomitant drug supplemental page)

Disease/Syndrome (specify)	Date of Onset (dd/mmm/yyyy)	Continuing	Pertinent details Include surgical procedures and dates
		 Yes  No  Unknown	
		 Yes  No  Unknown	
		 Yes  No  Unknown	
		 Yes  No  Unknown	
		 Yes  No  Unknown	
		 Yes  No  Unknown	
		 Yes  No  Unknown	
		 Yes  No  Unknown	

**SERIOUS ADVERSE EVENT REPORT FORM**  
**Neuro Zti cochlear implant-system Efficacy and Safety in Adults**

**LAB DATA SUPPLEMENTAL PAGE**

**LAB DATA TEST/EXAM FINDINGS**

List **only** relevant confirmatory test results for event (including autopsy results, medical imaging results, etc.) if available, source documents are considered relevant/necessary, please attach **after** transcribing results.

Test	Test date (dd/mmm/yyyy)	Test result	Test unit	Normal low	Normal high
Comments:					
Test	Test date (dd/mmm/yyyy)	Test result	Test unit	Normal low	Normal high
Test	Test date (dd/mmm/yyyy)	Test result	Test unit	Normal low	Normal high
Test	Test date (dd/mmm/yyyy)	Test result	Test unit	Normal low	Normal high
Test	Test date (dd/mmm/yyyy)	Test result	Test unit	Normal low	Normal high
Test	Test date (dd/mmm/yyyy)	Test result	Test unit	Normal low	Normal high
Test	Test date (dd/mmm/yyyy)	Test result	Test unit	Normal low	Normal high
Test	Test date (dd/mmm/yyyy)	Test result	Test unit	Normal low	Normal high
Test	Test date (dd/mmm/yyyy)	Test result	Test unit	Normal low	Normal high
Test	Test date (dd/mmm/yyyy)	Test result	Test unit	Normal low	Normal high
Test	Test date (dd/mmm/yyyy)	Test result	Test unit	Normal low	Normal high

EXPLANTATION REPORT FORM  
Neuro Zti cochlear implant-system Efficacy and Safety in Adults

**Appendix 5: EXPLANTATION REPORT FORM**

**EXPLANTATION REPORT FORM**  
**Neuro Zti cochlear implant-system Efficacy and Safety in Adult**

The implantable device could be explanted for technical or medical issues.

This explantation report form should be completed with a clinical support from Oticon Medical Neurelec and sent to Oticon Medical Neurelec whether the internal part is removed or remains in situ.

Date of filing: |\_\_|\_\_|/|\_\_|\_\_|\_\_|/|\_\_|\_\_|\_\_|

**SOURCE OF THE INCIDENT**

Please describe	
 Device failure	_____ _____ _____ _____
 Medical reason	_____ _____ _____ _____
 Other	_____ _____ _____ _____

Oticon representative contacted prior explantation:	Medical prior	 Yes  No comment: _____
---	------------------	--

**PATIENT INFORMATION & IMPLANT INFORMATION**

Center ID		
Subject ID		
Implantation date		
Explantation date		
Explanted device model	 Neuro Zti CLA	 NeuroZTI EVO
Explanted device serial number		
Sound processor serial number		

**EXPLANTATION REPORT FORM**  
**Neuro Zti cochlear implant-system Efficacy and Safety in Adult**

**CLINICAL REPORT**

Incident onset date: |\_\_|\_\_|/|\_\_|\_\_|\_\_|/|\_\_|\_\_|\_\_|

Incident report:

Medical reason which could be linked to the incident:

EABR testing performed	 Yes	 No
If yes, did Oticon Medical determine that device failed prior explantation	 Yes	 No

Integrity testing performed	 Yes	 No
If yes, did Oticon Medical determine that device failed prior explantation	 Yes	 No

Please document that the following has taken place:

	SAE reporting form completed and sent to Oticon Medical
	Vigilance report completed and sent to Oticon Medical
	Vigilance report completed and sent to local competent authority
	Other, please specify

Please document the medical reason for device explant (*multiple choice is possible*)

	Performance issue
	Electrode migration
	Electrode array misplacement

**EXPLANTATION REPORT FORM**  
**Neuro Zti cochlear implant-system Efficacy and Safety in Adult**

	Implant migration/extrusion
	Facial nerve stimulation
	Shocking with device ON/OFF ( please delete as appropriate )
	Pain and/or discomfort with device ON Precise location (e.g. over implant stimulator, ear canal, neck, etc.): _____
	Pain and/or discomfort with device OFF Precise location (e.g. scalp, flap, incision line, ear canal, neck, etc.): _____

**SURGICAL OBSERVATIONS during device explant**

Any physical signs of device failure prior explant?

Yes, please describe: \_\_\_\_\_  
 \_\_\_\_\_

No

Electrode status, did the electrode array appear to have moved since initial placement?

Yes, please describe: \_\_\_\_\_  
 \_\_\_\_\_

No

Any evidence of infection or tissue reaction?

Yes, please describe: \_\_\_\_\_  
 \_\_\_\_\_

No

Was a device re-implanted?

Yes, please precise, model and serial number: \_\_\_\_\_  
 \_\_\_\_\_

No

If yes, please describe the surgical placement of the second device

	Similar to placement of the first device
	Insertion with some resistance
	Partial / full insertion

**EXPLANTATION REPORT FORM**  
**Neuro Zti cochlear implant-system Efficacy and Safety in Adult**

	Other:   _____  _____  _____
--	--

Explanted device returned to Oticon Medical?

Yes

No, please explain: \_\_\_\_\_

---

Investigator
Authorized signature: _____
Print name: _____
Date:  __ __   __ __   __ __   __ __

## Appendix 6: CLINICAL SUPPORT ROLE

### 0. Purpose

This document describes the function and duties of the clinical support in this clinical trial. The main task of the clinical trial support is to make sure that medial team are properly used the Neuro cochlear implant system. The clinical trial support is an Oticon Medical employee, he/she have a background in audiology, speech therapy, PhD or engineer in audiology.

### 1. Scope

This document applies to the clinical trial which will be conducted in Canada and Denmark to support the PMA-FDA submission.

### 2. References

- Neurelec Clinical Support procedure (PG0005)

### 3. Abbreviation

eCAP: electrical Evoked Compound Action Potential

OR: Operating Room

### 4. Basic role of the clinical support

The clinical support provide clinical, expertise and support to Oticon Medical's participants' centers.

Provide clinical support, information and advice to clinical teams on topics such as surgery, and post-implantation management. Also, assist with clinical trial and research studies on Oticon Medical products.

The role focus on providing clinical expertise on product, support initial stimulation, assist with clinical problems, as well as performing training to build clinical capability through clinical investigation sites.

Cochlear implant centers must have the highest quality clinical and technical support available from the manufacturer.

### 5. Function and duties of technical support in this clinical trial

- Represents Oticon Medical during surgeries and cochlear implants by providing all necessary advice and support.
- Support the audiologist or its representative in conducting the objective measures (impedance and ECAPs) in the OR.
- Undertake eCAP and impedance measures in OR if there is nobody from the medical team dedicated for this task.
- Supervise eCAP and impedance measure in clinic.

- Evaluate the external, internal part or accessories for a better subject management.
- Provide expertise in all aspects of implant and troubleshooting techniques.
- Provides on-call support as needed for surgeries, reprogramming, troubleshooting, and follow-up on all visits.
- Support the audiologist or its representative in device fittings especially for the first one. The following fittings could be supervise by the clinical support at the request of the investigator site.
- Troubleshoot by testing and reprogramming device integrity testing and communicate the results to the managing audiologist.

## **6. Education support in this clinical trial**

- Educates and train surgeon and hospital team (hearing aid specialist, speech-pathologist, technician or audiologist) on technical matters relating to the cochlear implant system by conducting or coordinating:
  - o One on one training session
  - o In-service education programs
- Help audiologist in patient fittings
- Provide advice in and guidance to audiologist

## **7. What the clinical support Does Not Do in this clinical trial**

- Will never been alone with the patient, the patient is supported by the medical team involved in this clinical trial.
- Does not provides audiological assessment of patient
- Does not provides “switch-on” device programming of the recipient following surgery. The audiologist switch-on the device and the clinical support advice and guide the audiologist in the fittings.
- Does not provides routine ongoing device programming
- Does not carry out evaluation of candidate outcomes
- Does not undertake eCAP or impedance measures in clinic
- Does not interfere in management of recipient device repairs
- Does not interfere in management of recipient device accessories
- Does not interfere in equipment and products required for the device implant
- Does not provide recommendation about cochlear implant candidacy following assessment

## **Appendix 7: PATIENT HINT PERFORMANCE**

### **Preoperative evaluation**

- a) If the patient has a poor speech understanding in HINT-Q during the training (i.e. score of 0), it is recommended to performed the entire training list.

If the patient have a poor speech understanding in HINT-Q during the evaluation with a score of 0 words correctly repeated on the first six sentences:

- Stop the evaluation in Quiet
- Don't conduct the evaluation in Noise
- Record in the eCRF:
  - o HINT-Q raw score =0 , % correct = 0 and percent correct=0 for the 2 lists
  - o HINT-N raw score =0 , % correct = 0 and percent correct=0 for the 2 lists

- b) If the patient has a proper speech understanding in HINT-Q during the training, **AND**, the patient has a poor speech understanding during the evaluation with a score of 0 words correctly repeated on six consecutive sentences:
  - Give a short break to the patient, and when it's time, carry on with the evaluation
  - If the score still remains at 0 in the next 3 consecutive sentences, stop the evaluation.
  - Record in the eCRF the score of 0 in the respective input fields

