#### **At visit 2 (preoperatively)**

The test is conducted in quiet and in noise background, and in the best-aided conditions

In quiet:

The subject's is given practice sentences to become familiar with the task before each test. Then two 20-sentences lists of HINT shall be presented to the subject, in front (0° azimuth), in quiet at a conversational speech level of 60 dB SPL (Appendix 9: Calibration considerations). All words in the sentence repeated correctly, (Nilsson et al. 1994 [5]) shall be computed to calculate a score in percent correct of total words.

In noise:

As described above, the same procedure is applied for HINT-N, sentences are presented at +10dB SNR, with noise set at 55 dB SPL, and signal at 65 dB SPL.

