#### **c. HINT score calculation in quiet and noise conditions**

The ratio of words correctly repeated divided by the total of words for each list is multiplied by 100 to obtain the score in percent correct for the lists.

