### **Postoperative evaluation**

Please, see above

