## 5.6. Primary end point

### 5.6.1. HINT in Quiet at Month 6

Change from baseline to month 6 (refer to table 8).

Calculation = HINT-Q at Month 6 - HINT-Q at Inclusion visit

The primary efficacy endpoint of the Neuro CIS is assessed with the HINT score in quiet, on the ipsilateral ear.

The mean HINT scores in quiet will be used as the primary outcome measures for assessing the primary benefit.

The primary analysis will be performed on a subgroup of the FAS which consists of all English-speaking patients (Exclusion of Danish and French-Canadian speaking patients). The analysis will be replicated in PPS.

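### Appendix 7 rule (b) can record a HINT list as 0 after words were repeated correctly in it, which, read literally, does not fit the protocol's word-based score

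*Protocol*

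**What the plan says.** **Score definition.** Protocol 3.5.5.1 c defines the list score: "The ratio of words correctly repeated divided by the total of words for each list is multiplied by 100". The visit 2 procedure in 3.5.5.1 b says the same of the words repeated, which "shall be computed to calculate a score in percent correct of total words". Two lists of 20 sentences are given per condition.

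**Early stopping.** Appendix 7 has two rules.
- Rule (a) covers patients who do poorly in training. It is triggered by an evaluation "with a score of 0 words correctly repeated on the first six sentences", and it sets the quiet and noise scores to 0, naming both lists.
- Rule (b) covers patients who understood the training sentences. It is triggered by an evaluation "with a score of 0 words correctly repeated on six consecutive sentences". After a short break: "If the score still remains at 0 in the next 3 consecutive sentences, stop the evaluation". The recording line is "Record in the eCRF the score of 0 in the respective input fields".

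**After surgery.** The postoperative part of Appendix 7 reads only "Please, see above", so the same rules apply at 3, 6 and 12 months.

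**Analysis.** SAP 5.6.1 uses the recorded scores: "Calculation = HINT-Q at Month 6 - HINT-Q at Inclusion visit". SAP 6.1 adds a count of patients gaining at least 20 points. The eCRF items in SAP 2.1, the missing-data rules in SAP 3 and Table 8 do not identify a test that was stopped early.

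**The concern.** Rule (a) is tied to the start of the evaluation. Rule (b) is not: its run of zeros may begin anywhere. It also addresses patients who coped with the training sentences, so some correct words before the run are plausible. Nothing in rule (b) says that those words are kept. Nor does it say whether the respective fields are those of the stopped list, of both lists, or of the unpresented sentences only.

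If a site follows the wording literally, a real percent-correct score is replaced by 0. At inclusion this inflates the patient's change; at month 6 it deflates it. A recorded 0 is not missing, so the imputation rules do not touch it, and no planned table would show that it came from a stopped test. Two sites could enter different scores for identical responses.

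**Working it through.** **Inputs**
- List length 20 sentences, two lists per condition (Protocol 3.5.5.1 b).
- Zero run before the stop: 6 + 3 = 9 sentences (Appendix 7, rule b).
- List score = 100 × correct words / total words (3.5.5.1 c).
- Primary analysis size 39 and SD of change 25 (Protocol 3.6.1.4); one-sided α 0.025 (3.6.2.2).

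**Assumptions.** Equal sentence lengths; unpresented sentences count as 0 correct; the visit score is the mean of the two lists; all nine zero sentences fall in one list; one list is zeroed.

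**Step 1: when is the recorded 0 right?** With no correct word before the run, the formula gives 100 × 0 / total = 0. Rule (b) and the formula agree in that case only.

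**Step 2: range of scores overwritten.** At most 20 − 9 = 11 sentences can precede the run. With k fully correct sentences, the list score is 100 × k / 20 = 5k.

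| Correct before the run | Score by 3.5.5.1 c | Recorded, literal rule (b) | Loss on two-list mean |
|---|---|---|---|
| none | 0 | 0 | 0 |
| one word (5 words per sentence assumed, 100 per list) | 1 | 0 | 0.5 |
| 1 sentence | 5 | 0 | 2.5 |
| 4 sentences | 20 | 0 | 10 |
| 6 sentences | 30 | 0 | 15 |
| 11 sentences | 55 | 0 | 27.5 |

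The formula counts words, so the loss starts just above 0, not at one whole sentence.

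**Step 3: how typical is the top of the range?** It needs perfect sentences followed by nine with no correct word. In a simulation with constant ability (true score 2% to 30%, 4 to 6 words per sentence, within-sentence correlation of words from none to complete), affected lists lost about 1.4 to 12.6 list points on average. Averaged over all lists, the expected loss on the two-list mean was at most about 1.5 points per list. A loss of 30 or more list points had probability of at most about 0.4%. Small losses were not rare among very poor performers: up to about 40% of lists. Fatigue within a list was not modelled.

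**Step 4: group mean.** One affected patient moves the mean of 39 by at most 27.5 / 39 = 0.71 points. Five patients at that maximum, all in the same direction, move it by 5 × 27.5 / 39 = 3.53.

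**Step 5: primary test.** At SD 25 and n = 39 the mean change must exceed t(0.975; 38) × 25 / √39 ≈ 8.1. If one baseline list were overwritten at the maximum in all 39 patients, an observed mean of 50 would correct to 50 − 27.5 = 22.5, still well above 8.1. Losing significance would need an average overwrite of 50 − 8.1 = 41.9 points per patient, more than a single list can supply.

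**Step 6: responder count.** A zeroed baseline list turns a non-responder into a responder when the correct change lies below 20 by no more than the loss. A modest case: correct change 18, list loss 5, recorded change 18 + 2.5 = 20.5. A larger, rare case: baseline list 1 at 30%; list 2 with six correct sentences, then nine zeros. The formula gives (30 + 30) / 2 = 30; the literal rule gives (30 + 0) / 2 = 15. With 45 at month 6 the change is 15 or 30. Each flip moves the rate by 1/39 = 2.6 percentage points.

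**The case against.** The strongest reply is that the text is ambiguous rather than contradictory. The stop line speaks of a score that still remains at 0, and the next line of the score of 0. Both can be read as a running score that has been 0 from the start, which is what 3.5.5.1 c would give. Likewise, the respective fields could be only those for unpresented sentences, and the eCRF layout is not in the documents. Rules (a) and (b) are also separated by training performance, so the contrast between the first six and any six sentences does not settle the intent. This stands in part: a reader might infer a flat contradiction, and the documents support only a conflict under the literal reading. But no benign reading is written down, and the only fields that Appendix 7 names are list-level scores.

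A reader might also infer that a stop in list 2 zeroes both lists, so that the larger example in the working would have a baseline of 0 and a change of 45. That reading is strained: rule (a) names two lists and rule (b) does not.

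Finally, a reader might infer that the efficacy conclusion is at risk. It is not. Protocol 3.6.2.4 bases labeling claims on the primary analysis alone, and SAP 6.1 gives the 20-point count a descriptive role without a test. The rule applies before and after surgery, so errors go both ways. They need not cancel, because low scores are likelier at baseline.

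**Conclusion.** The recording line of rule (b) is wrong as written and should be reconciled with 3.5.5.1 c. Followed literally, it replaces a list score of more than 0 and up to 55% with 0, and understates the two-list mean by up to 27.5 points when one list is zeroed. These limits rest on the assumptions listed in the working. The upper end is an extreme, and typical losses would be much smaller.

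The number of stopped tests, and how sites read the rule, cannot be learned from the documents, so the net bias cannot be quantified. It is probably small on the mean. What is exposed is the size of the reported mean change and individual classifications in the responder count. The point is worth correcting because it concerns the primary measure, the correction is simple, and nothing now planned would reveal the problem.

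**What to change.** **Appendix 7, rule (b), recording line.** Suggested wording: *When a test is stopped early, record for each list the number of words actually repeated correctly over the total words of that list, counting unadministered sentences as 0. Leave the other list as scored. Flag the early stop in the eCRF.* The stopping triggers and rule (a) stay unchanged.

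**SAP.** Add one sentence: the number of early-stopped tests is reported by visit beside Table 8.

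**Tests already recorded.** Where sentence-level responses were retained, rescore tests entered as 0 under rule (b), by a written rule fixed before change scores are examined. Appendix 9, section 5, says the software helps to record responses; it does not say that they were kept. Appendix 7 came in with edition F (October 2017) and the stated start is January 2017, so check by test date which recording practice applied. List the tests that cannot be rescored. Any analysis that puts 0 to 55% on those lists should be labelled an extreme bound.

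**Cost.** One sentence in Appendix 7, one eCRF flag, one SAP sentence, and rescoring limited to recoverable tests. SAP version 3.0 (27/01/2020) postdates the planned completion in December 2019, so most tests may already be entered and some scores may be lost. For those, the count and the listing are what remains possible.

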### **Postoperative evaluation**

Please, see above

## Appendix 8: POST-OPERATIVE ECAP MEASUREMENT

When performing post-operative ECAP measurements, follow the guidelines/recommendations below:

As a minimum, perform ECAP on one electrode (electrode 18)  
If possible, perform ECAP on four electrodes (electrode 3, 8, 13, 18)

### Neuro ECAP

The Neuro ECAP 1.0® function allows to measure the electrophysiological responses of the auditory nerve by scanning with a range of Amplitude, for a fixed stimulation duration several electrodes.

Two modes are available:

**Basic:** where you can select the number of electrode to stimulate, the repetition frequency and the ECAP parameters (Minimum: Minimum Amplitude of the range tested, Maximum: Maximum Amplitude and Duration: Pulse Duration)

**Advanced:** where you can also choose the increment in the range of Amplitude tested, the stimulation and collection electrodes and the Number of repetitions for the measures.

**Attention:** Before setting the ECAP parameters during a post op. measurement, be sure to be lower than the C level of the patient.

#### If C levels are below 30 $\mu$ s

You should respect the following rule: C levels (perceived by the patient) are defined by an amplitude A and a duration T.

Then post op ECAP should have the following parameters:

Min 10

Max= A+5

Increment=2

Duration= T-10  $\mu$ s

For example, if patient is describing a sound as comfortable in a fitting window with an amplitude A of 20 and C of 25  $\mu$ s, then ECAP research on the corresponding electrode should be the following graph:

Depending on the patient perception, it is possible to go higher than those values or to stop the stimulation prior to that if auditory perception is too loud.

**If C levels are above 30  $\mu$ s**

You should respect the following rule: C levels (perceived by the patient) are defined by an amplitude A and a duration T.

Then post op ECAP should have the following parameters:

Min 10

[figure not shown]
Max= T - 5

Increment=3

Duration= A

Note : Max should not exceed 70 CU.

For example, if patient is describing a sound as comfortable on electrode 18 in a fitting window with an amplitude A of 23 and C of 45 $\mu$ s, then ECAP research parameters on the corresponding electrode should be the following graph:

On a general point of view, this post op ECAP protocol is meant to provide recommendations, the audiologist has a crucial role in the post op ECAP recording procedure as if the patient is describing a loud auditory sensation and the measurement is still running, then it is important to stop the recording to prevent the patient from receiving a too loud auditory sensation.

On the other side, if the patient is perceiving an auditory sensation that is considered as soft even at the MAX value, then the audiologist could decide to increase the MAX value.

